11.1.2 Serious Adverse Events

A SAE based on International Conference on Harmonisation (ICH) and EU Guidelines on Pharmacovigilance for Medicinal Products for Human Use is any untoward medical occurrence that at any dose:

- Results in death (ie, the AE actually causes or leads to death)
- Is life-threatening. Life-threatening is defined as an AE in which the subject was at risk of death at the time of the event. It does not refer to an event which hypothetically might have caused death if it were more severe. If either the investigator or the Sponsor believes that an AE meets the definition of life-threatening, it will be considered life-threatening.
- Requires in-patient hospitalization > 24 hours or prolongation of existing hospitalization
- Results in persistent or significant disability/incapacity (ie, the AE results in substantial disruption of the subject's ability to conduct normal life functions)
- Is a congenital anomaly/birth defect
- Is an important medical event that may not result in death, be immediately life-threatening or require hospitalization, but may be considered an SAE when, based upon appropriate medical judgment, the event may jeopardize the subject or

subject may require intervention to prevent one of the other outcomes listed in this definition. Examples of such events are intensive treatment in an emergency department or at home for allergic bronchospasm, blood dyscrasias, or convulsion that does not result in hospitalization; or development of drug dependency or drug abuse

Given that the investigator's perspective may be informed by having actually observed the event, and the Sponsor is likely to have broader knowledge of the drug and its effects to inform its evaluation of the significance of the event, if either the Sponsor or the investigator believes that the event is serious, the event will be considered serious.

11.1.3 Severity Criteria (Grade 1-5)

Definitions found in the Common Terminology Criteria for Adverse Events version 4.03 (CTCAE v4.03) will be used for grading the severity (intensity). The CTCAE v4.03 displays Grades 1 through 5 with unique clinical descriptions of severity for each referenced AE. Should a subject experience any AE not listed in the CTCAE v4.03, the following grading system should be used to assess severity:

- Grade 1 (Mild AE) experiences which are usually transient, requiring no special treatment, and not interfering with the subject's daily activities
- Grade 2 (Moderate AE) experiences which introduce some level of inconvenience or concern to the subject, and which may interfere with daily activities, but are usually ameliorated by simple therapeutic measures
- Grade 3 (Severe AE) experiences which are unacceptable or intolerable, significantly interrupt the subject's usual daily activity, and require systemic drug therapy or other treatment
- Grade 4 (Life-threatening or disabling AE) experiences which cause the subject to be in imminent danger of death
- Grade 5 (Death related to AE) experiences which result in subject death

11.1.4 Causality (Attribution)

The investigator is to assess the causal relation (ie, whether there is a reasonable possibility that the study medication caused the event) using the following definitions:

Not Related: Another cause of the AE is more plausible; a temporal sequence cannot be

established with the onset of the AE and administration of the

investigational product; or, a causal relationship is considered biologically

implausible.

The current knowledge or information about the AE indicates that a **Unlikely:**

relationship to the investigational product is unlikely.

There is a clinically plausible time sequence between onset of the AE and **Possibly** Related:

administration of the investigational product, but the AE could also be

attributed to concurrent or underlying disease, or the use of other drugs or procedures. Possibly related should be used when the investigational

product is one of several biologically plausible AE causes.

The AE is clearly related to use of the investigational product. **Related:**

11.2 Unexpected Adverse Events

An "unexpected" AE is an AE that is not listed in the ibrutinib IB/package insert or is not listed at the specificity or severity that has been observed. For example, hepatic necrosis would be "unexpected" (by virtue of greater severity) if the ibrutinib IB referred only to elevated hepatic enzymes or hepatitis. Similarly, cerebral thromboembolism and cerebral vasculitis would be "unexpected" (by virtue of greater specificity) if the ibrutinib IB/package insert listed only cerebral vascular accidents. "Unexpected" also refers to AEs that are mentioned in the ibrutinib IB as occurring with a class of drugs or as anticipated from the pharmacological properties of the drug, but are not specifically mentioned as occurring with the study drug under investigation.

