The incidence of TLS in NHL studies is low with reports of 2 cases (1.9%) of laboratory TLS in monotherapy Study M12-175, 4 cases of laboratory TLS (2.5%) in combination Study BO29337 (1 subject venetoclax + R, 3 subjects venetoclax + BR), and 4 cases of laboratory TLS (1.5%) in combination Study GO27878 (venetoclax + R-CHOP or G-CHOP). All cases of TLS resolved, and none led to discontinuation of study drug. No cases of clinical TLS were reported. Neutropenia has a similar frequency in the NHL clinical program as in CLL with higher frequency in NHL combination studies. Serious adverse events of neutropenia and febrile neutropenia, albeit in small numbers, occurred in higher frequency in combination studies. Infections, including serious, were observed in the NHL clinical program, with similar incidence in monotherapy and combination studies.

For the most comprehensive venetoclax safety and efficacy data, please refer to the most current venetoclax IB.

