2.2 Randomization Phase

2.2.1 Primary Objective

To evaluate whether the combination of ibrutinib and venetoclax will result in prolongation of PFS compared to ibrutinib and placebo in subjects with relapsed or refractory MCL.

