3.1.1 Safety Run-in Period

The study will start with an open-label Safety Run-in Period to evaluate the occurrence of TLS and DLTs with the concurrent administration of ibrutinib and venetoclax. TLS and DLT occurrence will be assessed during the venetoclax Ramp-up Period for a minimum of 5 weeks.

Up to 27 subjects may be enrolled during the Safety Run-in Period (Figure 6).

Figure 6. Study Schematic – Safety Run-in Period

PD = progressive disease; WC = withdrawal of consent

Tumor Lysis Syndrome (TLS) Categories

Two TLS risk categories will be evaluated separately and in parallel:

- Increased risk for TLS Subjects with high tumor burden (at least one lesion > 10 cm; or at least one lesion > 5 cm and circulating lymphocytes > 25,000 cells/mm³) and/or with baseline creatinine clearance (CrCl) < 60 mL/min. During the Safety Run-in Period, subjects at increased risk for TLS will be hospitalized for a minimum of 24 hours (and up to 48 hours at the discretion of the investigator) at the start of the 20 mg ramp-up dose and again at the start of the 50 mg ramp-up dose of venetoclax for monitoring and prophylaxis of TLS.
- Low risk for TLS Subjects not meeting the criteria described above.

TLS events are defined as follows:

- Clinical TLS any event that meets Howard criteria (Appendix G) with the following exceptions:
 - For the purpose of TLS assessment during the Safety Run-in Period, only those increases in serum creatinine > 1.0 mg/dL from pre-treatment baseline will be considered clinical TLS.
 - In subjects with renal dysfunction at baseline (CrCl < 60 mL/min), clinical TLS is defined as the presence of laboratory TLS plus either seizures, cardiac dysrhythmia, or death.
- Laboratory TLS any event that meets Howard criteria (Appendix G) for laboratory TLS, that does not resolve within 72 hours despite protocol required management.

Dose-Limiting Toxicity (DLT)

A DLT is defined as any Grade 3 or higher non-TLS AE at least possibly related to study drug (ibrutinib and/or venetoclax) and occurring during the DLT assessment period with the following clarifications:

Non-Hematologic DLTs:

[figure not shown]
- Grade ≥ 3 nausea, vomiting or diarrhea uncontrolled despite maximum medical supportive care and persisting > 5 days
- Grade 3 fatigue persisting > 7 days
- Grade 3 infection is not a DLT, however an infection with life-threatening consequences or requiring urgent intervention (Grade 4) will be considered a DLT

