5.3.2 Venetoclax

5.3.2.1 Formulation/Packaging/Storage

The individual study drug information is presented in Table 4.

Table 4. Identity of Venetoclax/Placebo Drug Product

Study Drug	Trademark	Formulation	Route of Administration	Manufacturer
Venetoclax/placebo	N/A	10 mg tablet Film coated	Oral	AbbVie
Venetoclax/placebo	N/A	50 mg tablet Film coated	Oral	AbbVie
Venetoclax/placebo	N/A	100 mg tablet Film coated	Oral	AbbVie

Packaging and Labeling

The venetoclax/placebo tablets will be packaged in blister packs during the initial dose ramp-up period and in high density polyethylene (HDPE) plastic bottles thereafter to accommodate the study design. Each container will be labeled as required per country requirements. Labels must remain affixed to the container.

Storage and Disposition of Study Drug

The venetoclax/placebo supplied in this study is for investigational use only, and must only be used within this study. All study drug must be maintained under adequate security and stored under conditions specified on the label until dispensed for subject use or returned to the Sponsor or representative.

The tablets must be stored at a controlled room temperature of 15° to 25°C (59° to 77°F).

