11.4 Documenting and Reporting of Adverse Events and Serious Adverse Events by Investigators

11.4.1 Assessment of Adverse Events

Investigators will assess the occurrence of AEs and SAEs at all subject evaluation timepoints during the study. All AEs and SAEs, whether volunteered by the subject, discovered by study personnel during questioning, detected through physical examination, clinically significant laboratory test, or other means, will be recorded in the subject's medical record and on the AEs CRF and, when applicable, on the Serious Adverse Event Report Form.

Each recorded AE or SAE will be described by its duration (ie, start and end dates), severity, regulatory seriousness criteria (if applicable), suspected relationship to the investigational product, and any actions taken.

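### Protocol 11.2 judges expectedness only against the ibrutinib reference documents, so events attributed to venetoclax can be misclassified in either direction

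*Protocol*

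**What the plan says.** Protocol 11.2 defines an unexpected adverse event as one that "is an AE that is not listed in the ibrutinib IB/package insert or is not listed at the specificity or severity" that was observed. The section names the ibrutinib documents four times: in the definition, in the hepatic example, in the cerebrovascular example and in the closing sentence on class effects. It does not mention venetoclax.

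Elsewhere venetoclax is treated as a study drug in its own right:

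- Protocol 3.1.1 requires a dose-limiting toxicity to be "at least possibly related to study drug (ibrutinib and/or venetoclax"). SAP section 1 likewise uses study drug to mean both ibrutinib and venetoclax or placebo.
- Protocol 5.3.2.1 states: "The venetoclax/placebo supplied in this study is for investigational use only".
- Under Protocol 2.2.1, the randomized comparison asks whether the "combination of ibrutinib and venetoclax will result in prolongation of PFS compared to ibrutinib and placebo in subjects with relapsed or refractory MCL". Ibrutinib is in both arms; venetoclax/placebo is what differs.
- Protocol 1.3.2.2 directs the reader to a separate document: "For the most comprehensive venetoclax safety and efficacy data, please refer to the most current venetoclax IB". Section 13 lists that IB alongside the ibrutinib one.

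The causality text is also written for a single product. Protocol 11.1.4 grades relatedness to one investigational product, and 11.4.1 asks for the "suspected relationship to the investigational product, and any actions taken".

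**The concern.** Expectedness compares an observed event with what is already known about the suspected drug. With two study drugs and one reference, events attributed to the second drug are compared with the wrong list. The omitted drug is the one whose added effect the randomized phase tests, and the reference used belongs to the background drug given in both arms.

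At stake is the correct labelling of individual related events, and any onward report that depends on that label. Two errors are possible. An event new for venetoclax may be labelled expected because ibrutinib has it, or an event already known for venetoclax may be labelled unexpected because ibrutinib lacks it.

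**Working it through.** There is no figure to reproduce; this is a reading of the text.

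**Step 1. Is there a second expectedness rule?** Protocol 11.1 to 11.4 contains none outside 11.2. The venetoclax IB is cited for pharmacokinetics (1.3.2.1), safety background (1.3.2.2) and drug interactions (6.2.1.2, 6.2.3), but never for expectedness. SAP section 5 does not use expectedness. The class-effect sentence in 11.2 widens the definition, but only by reference to what the ibrutinib IB says.

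**Step 2. Apply 11.2 to an event attributed to venetoclax alone.** Here listed means listed at the observed specificity and severity.

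| Ibrutinib document | Venetoclax IB | Result under 11.2 | Result against venetoclax IB |
|---|---|---|---|
| Listed | Listed | Expected | Expected |
| Listed | Not listed | Expected | Unexpected |
| Not listed | Listed | Unexpected | Expected |
| Not listed | Not listed | Unexpected | Unexpected |

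The second and third rows disagree. For an event attributed to ibrutinib alone, 11.2 uses the right reference. For an event attributed to both drugs and listed only for ibrutinib, 11.2 gives expected, although the event is not listed for one of the suspected drugs.

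**Step 3. Do the documents give examples?**

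- Listed for ibrutinib only: bleeding, interstitial lung disease, and cardiac arrhythmia or failure appear among the ibrutinib risks (1.2.4.1, 1.2.4.5, 1.2.4.6) but not among the venetoclax risks (1.3.3). These illustrate the second row but do not prove it. Section 1.3.3 is a summary, 1.3.2.2 mentions further venetoclax events such as nausea, diarrhea and thrombocytopenia, and neither IB is available here.
- Listed for venetoclax only: no example. The three venetoclax risks in 1.3.3 (tumor lysis syndrome, neutropenia, serious infection) have ibrutinib counterparts in 1.2.4.7, 1.2.4.4 and 1.2.4.3.

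**Step 4. How many subjects does the rule cover?** Of about 260 randomized 1:1, 260 / 2 = 130 are planned to receive venetoclax. Adding up to 27 in the safety run-in and about 75 treatment-naive subjects gives 130 + 27 + 75 = 232. This counts exposed subjects, not misclassified events.

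**Step 5. What depends on the label?** The protocol attaches no explicit action to an event being unexpected. Under 11.4.3, investigators send every SAE within 24 hours, and onward reporting is left to the sponsor under local rules.

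**The case against.** The strongest case against the point is that 11.2 drives little that can be seen in these documents. All SAEs reach the sponsor within 24 hours whatever their expectedness (11.4.3). Major hemorrhage goes on the SAE form within the same time even when not serious (11.4.7). The DMC reviews unblinded safety data, including all deaths (3.1.2). SAP section 5 tabulates hemorrhage, atrial fibrillation, interstitial lung disease, tumor lysis syndrome, infections and cytopenias by arm. Because ibrutinib is in both arms, an excess due to venetoclax would show as a between-arm difference regardless of what either label lists. All of this stands.

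A reader might therefore infer too much in three ways:

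- **That a new venetoclax safety signal would go unseen.** The documents do not support this. Detection runs through the routes above, and 11.2 still flags an event that exceeds the listed specificity or severity.
- **That particular events, such as atrial fibrillation, would in fact be misclassified.** That depends on the two IBs, which are not in the documents.
- **That attribution by drug is not collected.** The AE form is not in the documents, and 5.3.1.4 and 5.3.2.5 already require ibrutinib-related and venetoclax/placebo-related toxicities to be distinguished for dose modification. The single-product wording in 11.1.4 and 11.4.1 is an inconsistency, not proof of a missing field.

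The sponsor's procedures, which section 11 says follow regulatory requirements, may also apply a venetoclax reference document. They may, but neither section 11 nor 11.4.3 names one or says that 11.2 is overridden. Over-flagging events listed only for venetoclax is the cautious error. None of this removes the omission: 11.2 is the only expectedness rule that the protocol gives, and its wording yields the wrong class in the two discordant cases.

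**Conclusion.** The point holds, as a minor but real correction to safety wording. Section 11.2 states a rule that omits one of two study drugs, and that rule misclassifies some combinations of attribution and listing. The consequence is limited to expectedness classification and any onward reporting that relies on it. No endpoint, estimand, alpha, sample size or planned safety table is affected.

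The rule applies to about 232 subjects planned to receive venetoclax, but the number of events affected cannot be derived. The conclusion assumes that 11.2 is applied as written; if sponsor procedures already use the venetoclax IB, the defect is that the protocol disagrees with practice. The stronger conclusion that venetoclax signals are suppressed is not supported.

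**What to change.** Amend 11.2 so that expectedness is judged separately for each suspected study drug against that drug's own reference: the ibrutinib IB/package insert for ibrutinib and the venetoclax IB for venetoclax/placebo. State that a related event unexpected for any suspected drug is handled as unexpected. Reword the two examples and the class-effect sentence to match.

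Align 11.1.4 and 11.4.1 so that causality is stated for each study drug. Change the AE form only if it does not already record this.

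The cost is protocol wording, possibly one form field, and slightly more expectedness assessments. No treatment, endpoint or analysis changes.

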11.3 Special Reporting Situations

Special reporting situation on a Sponsor study may require expedited reporting and/or safety evaluation include, but are not limited to:

- Overdose of any study drug
- Suspected abuse/misuse of a study drug
- Inadvertent or accidental exposure to a study drug
- Medication error involving a product (with or without subject exposure to the study drug, eg, name confusion)

If any special reporting situation meets the criteria of an AE, it should be reported on the Serious Adverse Event Report Form. Please report all overdoses on a SAE form regardless of the

outcome. The Serious Adverse Event Report Form should be sent via email or fax to Pharmacyclics LLC Drug Safety or designee within 24 hours of awareness.

11.4 Documenting and Reporting of Adverse Events and Serious Adverse Events by Investigators

11.4.1 Assessment of Adverse Events

Investigators will assess the occurrence of AEs and SAEs at all subject evaluation timepoints during the study. All AEs and SAEs, whether volunteered by the subject, discovered by study personnel during questioning, detected through physical examination, clinically significant laboratory test, or other means, will be recorded in the subject's medical record and on the AEs CRF and, when applicable, on the Serious Adverse Event Report Form.

Each recorded AE or SAE will be described by its duration (ie, start and end dates), severity, regulatory seriousness criteria (if applicable), suspected relationship to the investigational product, and any actions taken.

11.4.2 Adverse Event Reporting Period

All AEs whether serious or non-serious, will be documented from the time the signed and dated ICF is obtained until 30 days following the last dose of study drug. SAEs will be reported to the Sponsor Drug Safety via an SAE reporting form and will be recorded in the eCRF from the time of ICF signing. Non-serious AEs will be recorded in the source documents from the time of ICF signing and will be recorded in the eCRF from the first dose of study drug.

Serious adverse events reported after 30 days following the last dose of study drug should also be reported if considered related to study drug. Resolution information after 30 days should be provided.

Progressive disease should NOT be reported as an event term, but instead symptoms/clinical signs of disease progression may be reported (see Section 11.1.1).

All AEs, regardless of seriousness, severity, or presumed relationship to study drug, must be recorded using medical terminology in the source document. All records will need to capture the details of the duration and the severity of each episode, the action taken with respect to the study drug, investigator's evaluation of its relationship to the study drug, and the event outcome. Whenever possible, diagnoses should be given when signs and symptoms are due to a common etiology (eg, cough, runny nose, sneezing, sore throat, and head congestion should be reported as "upper respiratory infection"). Investigators must record in the CRF their opinion concerning the relationship of the AE to study therapy. All measures required for AE management must be recorded in the source document and reported according to Sponsor instructions.

All deaths should be reported with the primary cause of death as the AE term, as death is typically the outcome of the event, not the event itself. Autopsy and postmortem reports must be

FINAL

forwarded to the Sponsor, or designee, as outlined above, if allowed per local regulatory guidelines.

If a death occurs within 30 days after the last dose of study drug, the death must be reported to the Sponsor as a SAE.

11.4.3 Expediting Reporting Requirements for Serious Adverse Events

All SAEs (initial and follow-up information) will be reported on the Serious Adverse Event Report Form and sent via email or fax to Pharmacyclics LLC Drug Safety, or designee, within 24 hours of the discovery of the event or information. Pharmacyclics LLC may request follow-up and other additional information from the investigator (eg, hospital admission/discharge notes and laboratory results). The contact information (phone, email and fax) for Pharmacyclics LLC Drug Safety can be found on the Serious Adverse Event Report Form and instructions.

All SAEs that have not resolved by the end of the study, or that have not resolved upon discontinuation of the subject's participation in the study, must be followed until any of the following occurs:

- The event resolves
- The event stabilizes
- The event returns to baseline, if a baseline value/status is available
- The event can be attributed to agents other than the study drug or to factors unrelated to study conduct.
- It becomes unlikely that any additional information can be obtained (subject or health care practitioner refusal to provide additional information, lost to follow up after demonstration of due diligence with follow-up efforts)

The Sponsor assumes responsibility for appropriate reporting of AEs to the regulatory authorities and governing bodies according to the local regulations.

The investigator (or Sponsor where required) must report these events to the appropriate Independent Ethics Committee/Institutional Review Board (IEC/IRB) that approved the protocol unless otherwise required and documented by the IEC/IRB.

